7.3.1 Laboratory Data in the Maximal Use Arm

Laboratory results from subjects in the maximal use arm will be listed separately.

7.4 Vital Signs

Vital sign parameters will include temperature, systolic and diastolic blood pressure, heart rate, and respiration rate. The actual value and change from baseline to each on-study evaluation will be summarized using descriptive statistics using the primary safety data presentation for each vital sign parameter. Measurements that are unscheduled and that do not fall in a protocol-specified visit window will not contribute to the summary tabulations.

Vital sign measurements and changes from baseline will be presented for each subject a data listing.

7.4.1 Vital Signs in the Maximal Use Arm

All vital sign data for subjects in the maximal use arm will be listed separately.

7.5 Physical Examination

Any new abnormalities in physical examination deemed clinically significant will be reported as an adverse event. All physical examination data will be presented in a by-subject data listing.

7.5.1 Physical Examination in the Maximal Use Arm

All physical examination data for subjects in the maximal use arm will be listed separately.

7.6 Prior and Concomitant Medications

Prior and concomitant medications will be coded using the WHO Drug Dictionary Version March 2022. Results will be tabulated by anatomic therapeutic class (ATC) and preferred term. Subjects will be counted only once by ATC and preferred term. Missing and partial dates will be handled as described in Section 3.9.3.

Concomitant medications are defined as any medication that did not end prior to first application of study drug. Prior medications consist of all medication that ended prior to the first application of study drug. If an end date is missing or the medication is ongoing, the medication will be considered both prior and concomitant.

A summary of prior medication used to treat CI will be provided as well.

The use of prior and concomitant medications will be included in a by-subject data listing. A listing of prohibited medications will also be provided; prohibited medications can be found in Table 7 of the study protocol.

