6.5 Concomitant Therapy

Prohibited medication and treatments including the washout periods are summarized in Table 7.

- Non-petrolatum bland emollients^a and OTC low potency hydrocortisone (e.g., 1% cream) may only be used in the event of severe discomfort (e.g., burning/erythema/itch) (after Week 3 in the Phase III study and during the entire time in the Optional Maximal Use arm) and if it is the opinion of the Investigator that a drug interruption (per [Section 7.1](#))

^a Subjects enrolled in the study will use mandatory bland emollients during the Induction Period (1-3 weeks). After the Induction Period, bland emollients will be prohibited for these subjects until the EOS visit. Subjects enrolled into the Optional Maximal Use arm should discontinue the use of bland emollients at Visit 2 (Baseline).

alone will not relieve the symptoms and these may cause the subject to discontinue from study. The duration of the mitigation plan should not exceed 2 weeks.

- Topical antibiotic or antifungal treatments can be used after consultation and at the discretion of the Investigator. Systemic antifungals or antibiotics must be prescribed by the Investigator if necessary to avoid risk of more serious or broader infections.
- Subjects should limit exposure to UV via sunlight and avoid tanning beds.

Table 7 Prohibited Medication and Treatments Including Time Point of Discontinuation

Prohibited Medication	Time Point of Discontinuation

 • Topical retinoids • Topical prescription or over-the-counter therapies 	2 weeks before Visit 2 (Baseline)

 • Keratolytics • Topical corticosteroids 	5 days before Visit 2 (Baseline)

 • Bland emollients 	
 • Visit 2 (Baseline) – for Optional Maximal Use arm • Visit 4 (Week 4) – for Phase III study
• Over-the-counter low potency hydrocortisone	Visit 2 (Baseline)
Prohibited Systemic Treatment	Time Point of Discontinuation

 • Systemic retinoids 
 ◦ Isotretinoin ◦ Acitretin 	
 • 12 weeks before Visit 2 (Baseline) – for Optional Maximal Use arm • 1 year before Visit 2 (Baseline) – for Phase III study • 3 months before Visit 2 (Baseline)

 • Vitamin A supplements • St. John's Wort • Other therapies intended for CI or may improve CI 	4 weeks before Visit 2 (Baseline)

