• Immunosuppressive drugs (e.g., systemic corticosteroids)	2 weeks before Visit 2 (Baseline)
Other	Time Point of Discontinuation
• Ultraviolet treatment	4 weeks before Visit 2 (Baseline)

Subjects may not be enrolled in an investigational drug or device study or have used an investigational drug or investigational device treatment within 30 days prior to Visit 2 (Baseline).

Any medication or vaccine (including OTC or prescription medicines, vitamins, and/or herbal supplements) that the subject is receiving at the time of enrollment or receives during the study must be recorded on the eCRF along with:

- Reason for use;
- Dates of administration including start and end dates; and,
- Dosage information including dose and frequency.

The Medical Monitor should be contacted if there are any questions regarding concomitant or prior therapy.

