3.5 Subgroups of Interest

Descriptive subgroup analyses may be performed by age group (6-11 years, 12-16 years, ≥ 17 years), and genetic subtype (RXLI, ARCI) on select safety endpoints.

Additionally, the following subgroups may be explored for both efficacy and safety parameters:

- Prior use of retinoids (Yes, No)
- Body Surface Area (BSA) Treated (\geq median, $<$ median)
- Age group (pediatric [≤ 17 years], adult [≥ 18 years])
- Remote Visits (no remote visits, ≥ 1 remote visit [excluding Visit 3 and Visit 8, which are per-protocol remote visits])
- Gender (male, female)
- Race (white, black or African American, Asian, other)

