3.9.3 Prior and Concomitant Medication Data

When tabulating prior/concomitant medication data, partial start dates will be handled as follows:

- If the year, month, and day are all missing, then set the start date to the date of first dose.
- If the month and day are missing and the year is earlier than the year of the first dose, then set the start date to December 31. Otherwise, set the start date to the date of first dose.
- If only the day is missing, if the month/year is earlier than the month/year of the first dose then set the start date to the first day of the month. Otherwise, set the start date to the last day of the month.

Partial end dates will only be imputed if the year is non-missing:

- If the month and day are missing then set the end date to December 31.
- If only the day is missing, then set the end day as the last day of the month.

If the imputed start date is later than the imputed end date then set the imputed start date to the imputed end date.

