4.3 Baseline Disease Characteristics

The type of CI (both as reported in the IRT and in the EDC) and specific mutation will be tabulated, in addition to whether the test was performed prior to or as part of the screening portion of the study. The time since initial clinical diagnosis of CI, as well as

the total percent body surface area (BSA) affected with CI will be summarized using descriptive statistics.

Prior medications specific for the treatment of CI will be tabulated, such as the use of over-the-counter products and emollients, oral retinoids, UV light, systemic corticosteroids, and topical retinoids.

All baseline disease characteristics will be provided in by-subject data listings.

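### SAP 7.6 labels a medication as prior on its end date alone, so a drug first taken on study and still ongoing is tabulated as prior

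*SAP*

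**What the plan says.** SAP 7.6 gives three sentences on classification.

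- Prior: "Prior medications consist of all medication that ended prior to the first application of study drug".
- Concomitant: "Concomitant medications are defined as any medication that did not end prior to first application of study drug".
- Open-ended records: "If an end date is missing or the medication is ongoing, the medication will be considered both prior and concomitant".

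The section refers to SAP 3.9.3 for missing and partial dates. On end dates, 3.9.3 says: "Partial end dates will only be imputed if the year is non-missing". It also imputes missing and partial start dates, but 7.6 does not use a start date to classify anything. Protocol 6.5 requires both start and end dates for every medication in use at enrolment or received during the study.

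Prior medication is used or named in three places: the prior-medication table and the summary of prior CI treatment in 7.6; SAP 4.3, Baseline Disease Characteristics ("Prior medications specific for the treatment of CI will be tabulated"); and SAP 3.5, which lists prior retinoid use (yes or no) among subgroups that may be explored. Neither 4.3 nor 3.5 names its data source. The addendum to SAP Version 3.0 leaves 7.6 unchanged.

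**The concern.** The first two sentences of 7.6 form a clean, mutually exclusive split. The third overrides it. An ongoing medication has, by definition, not ended before first application, so it fails the SAP's own test for prior and is nevertheless counted as prior. Because no start date is checked, this applies equally to a drug used for years before Baseline and to one first taken in Week 8.

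At stake is what the prior-medication tables mean. SAP 4.3 presents prior CI treatment as a baseline characteristic. A table read that way should not contain treatment begun after randomization, and a reader of the study report could not tell which entries were.

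**Working it through.** No figure in the plan is at issue. The check applies the rule to every possible date pattern.

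**Notation.** S = start date, E = end date, D = date of first application.

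- SAP 7.6 as written: prior if E < D, or if E is missing or the drug is ongoing. Concomitant if E ≥ D, or if E is missing or the drug is ongoing.
- Start-date rule: prior if S < D. Concomitant exactly as in 7.6.

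| Start | End | SAP 7.6: prior / concomitant | Start-date rule: prior / concomitant |
|---|---|---|---|
| before D | before D | yes / no | yes / no |
| before D | on study | **no** / yes | **yes** / yes |
| before D | ongoing or missing | yes / yes | yes / yes |
| on study | on study | no / yes | no / yes |
| on study | ongoing or missing | **yes** / yes | **no** / yes |

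**Reading the table.**

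1. The last row is the error: a drug first taken on study is called prior because it has no end date.
2. Rows two and three show the related inconsistency. The same pre-baseline drug is prior if left ongoing and not prior if stopped on study.
3. The concomitant class is identical under both rules in all five rows. Only the prior label changes.

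**Do the date rules in 3.9.3 repair it?** Only in part. An end date with a known year is imputed, so it no longer counts as missing. An ongoing record, or one with no end year, still falls under the third sentence of 7.6. The imputed start date is never brought into the classification.

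**Which on-study records are exposed?** Only those open at last contact or lacking an end year. The schedule of assessments (Protocol 1.2, Table 1) collects concomitant medication through Visit 9 and not at the Visit 10 safety follow-up. A treatment begun shortly before the last collection can therefore remain open in the data. So can any long-term drug started on study.

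**Would a bare start-date rule be safe?** No. Under 3.9.3:

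- a wholly missing start date is set to D;
- a start known only to the year is set to D unless that year is earlier than the year of first dose;
- a start missing only the day, in the month of first dose, is set to the last day of that month.

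Each of these lands on or after D. A long-standing ongoing treatment with such a start date would then become concomitant only and lose a prior label that 7.6 now gives it.

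**The case against.** **The default is reasonable for the case it was probably written for.** If a drug began before dosing and its end date is unknown, nobody can say whether it ended before first application, and both is a cautious choice. Calling a drug stopped in Week 2 concomitant only is likewise a definition and not, taken alone, an error. Both points stand. They do not cover a drug whose recorded start is on study, where the prior label is simply wrong.

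**A reader might infer that treatment for skin reactions will generally fill the prior tables.** The documents do not support that. Protocol 6.5 says of emollient and hydrocortisone use: "The duration of the mitigation plan should not exceed 2 weeks". Protocol 7.1 says such treatment stops once the reaction resolves. Most courses should carry an end date and stay concomitant only. The exceptions are courses open at last contact, which can occur: Appendix 11 allows topical corticosteroids for suspected allergic contact dermatitis in a patient who may then leave the trial. Nor do the documents establish an imbalance between arms, since Protocol 7.1 notes that reactions may also come from the vehicle.

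**A reader might also infer that post-randomization treatment can move subjects between the prior-retinoid subgroups.** That would need all of the following:

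- a retinoid, which Protocol Table 7 prohibits, first taken on study;
- no end date for it;
- no earlier retinoid use in that subject;
- a subgroup flag derived from the 7.6 class, which the SAP does not state.

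The list in SAP 4.3 includes UV light, which is not a drug. This hints at a separate source for prior CI treatment but does not prove one. The subgroup is also optional.

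**Conclusion.** The defect is real and can be read directly from the text: a stated rule gives a wrong table entry and contradicts the sentence before it. It affects medications with a recorded start on or after first application that are ongoing or have no end year. A related inconsistency affects pre-baseline drugs stopped on study.

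The consequence is small. It reaches the descriptive prior-medication table and, only if they are built from this class, the prior-CI-treatment summaries in SAP 7.6 and 4.3. The primary and key secondary tests do not use the prior class. Their stratification is by age and genetic subtype, and on-study prohibited medication is handled through the estimand (SAP 5.1.1 and 5.2.1), where it makes the subject a non-responder. Any effect on the prior-retinoid subgroup depends on a derivation that the SAP leaves open.

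The documents give no count of open-ended on-study records, so no number of affected subjects can be supported. The conclusion assumes that 7.6 will be programmed as written.

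**What to change.** Replace the classification text in SAP 7.6 with rules on both dates:

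- Prior: started before first application.
- Concomitant: not ended before first application.
- Both: started before and not ended before.
- Recorded start on or after first application: concomitant only, whatever the end date.

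Apply these to recorded start dates. Where the start is missing, or too partial to place before or after first application, keep the present default of both if the end date is missing or the drug is ongoing. Say in 3.9.3 that its imputed start dates do not override this.

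In SAP 3.5, state the source of the prior-retinoid flag and derive it only from use known to have started before first application. In 4.3, state whether the prior-CI-treatment table uses the 7.6 class.

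The cost is a few sentences across 7.6, 3.9.3, 3.5 and 4.3 and a small programming change. No new data are needed, because start dates are already collected.

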7.6.1 Prior and Concomitant Medications in the Maximal Use Arm

Prior and concomitant medications used by subjects in the maximal use arm will be provided in a separate by-subject data listing.

8.0 CHANGES TO PLANNED ANALYSES

The following are changes between the protocol-defined statistical analyses and those presented in this statistical analysis plan:

- The key secondary objective of ascertaining the efficacy of TMB-001 0.05% at Week 12 using the VIIS-50 scaling score has been moved to an other secondary objectives. Related endpoints and analyses have been updated accordingly. This change was made per FDA feedback.
- The key secondary objective for pruritus, i.e. evaluating the effect of TMB-001 0.05% at Week 12 using the Itch-Numeric Rating Scale (I-NRS), was clarified to instead use the Worst Itch-Numeric Rating Scale (WI-NRS) rather than the I-NRS. This change was made per FDA feedback.

10.0 CHANGE HISTORY

Version	Date	Description of Changes
1.0	02 March 2023	Original Final Version
1.1	10 May 2023	Added the inclusion of a DSMB; Added the analysis of topline data after Week 12.
2.0	12 May 2023	Updated eCRF version referenced; Second Final Version
2.1	15 January 2024	Added additional subgroup analyses by gender and race; Added estimand framework for other secondary endpoints; Added use of multiple imputation for other secondary endpoints; Included smaller edits throughout the document.
2.2	16 February 2024	Added additional sensitivity analysis for primary and key secondary endpoints; Clarified primary methods of analysis for other secondary endpoints; Clarified the pruritus key secondary objective.
3.0	27 February 2024	Third Final Version

11.0 APPENDICES
